### **4.2.3 Extent of Exposure and Treatment Compliance**

#### **4.2.3.1 Extent of Exposure**

Exposure to the double-blind IP will be summarized for treatment duration (in days), calculated as *date of the last dose of the double-blind IP taken - date of the first dose of the double-blind IP taken + 1* (Analysis Population: FAS).

Duration of exposure before and after implementing the CSP amendment 2 will also be summarized.

#### **4.2.3.2 Measurement of Treatment Compliance**

Dosing compliance for a given period is calculated as follows:

*100 × (total number of treatment applications [puffs] of the double-blind IP actually taken / number of treatment applications [puffs] of the double-blind IP expected to be taken) by a patient during a given period.*

The number of puffs actually taken is obtained from “Double Blind Study Drug Record” page of eCRFs.

The number of puffs expected to be taken in a given period is calculated as follows:

*2 × (End date - Start date + 1 for that period)*

i.e., a patient is expected to inhale 2 puffs per day. For those patients who complete the study, 1 puff is subtracted from the number of puffs expected to be taken since no evening dose is administered on the date of the last dose.

A patient is defined as compliant with treatment if treatment compliance rate is at least 75%.

Descriptive statistics for treatment compliance rate will be presented by treatment group for two periods (Analysis Population: FAS):

- Treatment period, and
- The first year of treatment.

Number and percentage of patients compliant with treatment will also be presented by treatment group for two periods above (Analysis Population: FAS).

#### **4.2.4 Efficacy analyses**

All efficacy analyses will be based on the FAS Population. All statistical tests will be two-sided hypothesis tests performed at the 0.05 significance level for main effects. All CIs will be two-sided 95% CIs. No multiplicity adjustment will be made to CIs as they will be interpreted descriptively and used as a measure of precision. All p-values will be unadjusted.

To control for multiplicity, the primary and secondary efficacy variables will be tested sequentially, i.e., the secondary efficacy endpoint will be tested only when both primary and secondary analyses on the primary efficacy endpoint achieved statistical significance, and the secondary analysis on the primary efficacy endpoint will be tested only when the primary analyses on the primary efficacy endpoint achieved statistical significance. Otherwise, nominal p-values will be provided and should be interpreted descriptively.

Analyses on COPD exacerbations will be based on definitions as described in Section 3.1.6.

#### 4.2.4.1 Primary efficacy outcome variable

The primary efficacy variable is rate of moderate or severe COPD exacerbation per patient per year during the first year of treatment. The primary analysis (on-treatment analysis) is to compare rate of moderate or severe COPD exacerbation per patient per year during the first year of treatment between aclidinium and placebo in patients in the FAS. Patients will be analyzed according to randomized treatment.

The null hypothesis is that the exacerbation rate on aclidinium is equal to the exacerbation rate on placebo. The alternative hypothesis is that the exacerbation rate on aclidinium is not equal to the exacerbation rate on placebo, i.e.:

$$H_0: \text{Rate ratio (aclidinium over Placebo)} = 1$$

versus

$$H_a: \text{Rate ratio (aclidinium over Placebo)} \neq 1$$

Exacerbation rate in aclidinium group will be compared to exacerbation rate in the placebo group using a negative binomial regression model. The response variable in the model will be the number of moderate or severe COPD exacerbations experienced by a patient during the first year of treatment. The model will include treatment group, baseline ICS use, baseline COPD severity, history of at least one exacerbation in the past year, and smoking status as factors. In order to adjust for the exposure for each patient, the natural logarithm of the exposure time (in years) during the first year of treatment will be used as an offset variable. When used as the offset variable, the exposure time will be adjusted by subtracting the time when a patient experienced COPD exacerbation(s) (i.e., not at risk during an exacerbation). The model is as follows:

*Number of moderate or severe exacerbations during the first year of treatment = treatment group + baseline ICS use + baseline COPD severity + history of at least one exacerbation in the past year + smoking status*

The estimated treatment effect (i.e., the rate ratio of aclidinium over placebo), corresponding 95% CI, and two-sided p-value for the rate ratio will be presented. In addition, the exacerbation rate and the corresponding 95% CI within each treatment group will be presented.

If the Negative Binomial regression model does not converge, the Poisson regression model with robust variance estimate using sandwich method will be applied. A scale parameter will be included to take overdispersion into account in fitting Poisson regression model. This would be a similar SAS GENMOD model to the one used for the Negative Binomial, but will specify Poisson as the distribution and include a scale parameter (DSCALE).

The primary analysis on the primary efficacy endpoint will be based on on-treatment analysis. For those patients who prematurely discontinue IP during the first year of treatment and have follow-up assessments, the primary analysis described above will be based on the data (events) collected before treatment discontinuation.

The secondary analysis on the primary efficacy endpoint will be based on on-study analysis using the same model as for the primary analyses of the primary efficacy endpoint. For those patients who prematurely discontinue IP during the first year of treatment and have follow-up assessments, the secondary analysis will include the events collected during the PTFU period up to one year.

The individual exacerbation criteria (use of systemic corticosteroids, use of antibiotics, and inpatient hospitalization due to COPD) will also be analysed using the same method as the primary analysis for on-treatment analysis during the first year of treatment, and will be summarized descriptively for on-study analysis over the whole study period.

The frequency of events and descriptive statistics of moderate or severe COPD exacerbations will also be provided by analysis method and period:

- On-treatment analysis during the first year of treatment
- On-study analysis during the first year of treatment
- On-treatment analysis over the whole study period
- On-study analysis over the whole study period.

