### **1.3.2 Power for the primary efficacy endpoint: rate of moderate or severe exacerbations per patient per year during the first year of treatment**

The sample size of 4,000 patients after 1 year of treatment will have ~89% power to detect a reduction in the rate of moderate or severe COPD exacerbations per patient per year during the first year of treatment of 14% (rate ratio of 0.86 in acclidinium bromide relative to placebo) at 0.05 significance level. The 89% power was calculated assuming a treatment discontinuation rate of 30% during the first year, a placebo rate of 0.8 exacerbation per patient per year (reduced from 1 to 0.8 as not all patients will have a history of exacerbation prior to randomization), and an overdispersion factor  $k$  of 0.67 (Keene et al, 2007).

See Section 9.7.9 of the CSP for detailed information on determination of sample size and power calculation.

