Group	Exacerbation history	CAT at baseline
A	0 or 1 (not leading to hospital admission)	<10
B	0 or 1 (not leading to hospital admission)	≥10
C	≥2 or ≥1 leading to hospital admission	<10
D	≥2 or ≥1 leading to hospital admission	≥10

Therefore, there are 16 potential categories with A, B, C and D phenotypes being further subdivided by 4 severities of airflow obstruction.

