### **4.2.2.2 Other baseline characteristics**

Various baseline characteristics will also be summarized descriptively by treatment group (Analysis Population: FAS). These include medical and surgical histories, COPD history, smoking status and history, pre-bronchodilator and post-bronchodilator tests at Screening, FEV1 at baseline, CAT score at baseline, prior medications, and COPD related prior medications. No statistical tests will be performed.

**Medical and surgical histories** will be coded using the Medical Dictionary for Regulatory Activities (MedDRA), version 18.0 or newer, and will be summarized by MedDRA SOC, HLT and PT. It will also be summarized in a separate table before and after implementing the protocol amendment 2.

COPD **history** will be summarized as follows:

- Duration of COPD in years

- Patient known to have either chronic bronchitis or emphysema (Yes, No)
- COPD exacerbation in the previous 12 months (Yes, No)
- Number of COPD exacerbations in the previous 12 months
- COPD severity based on airflow obstruction
- Combined assessment of COPD per GOLD (see Section 3.1.3 for categories)

COPD history will also be summarized in a separate table before and after implementing the protocol amendment 2

**Smoking status and history** will be summarized as follows:

- Smoking status
- Smoking duration in years
- Number of cigarettes per day
- Total pack-years

Smoking status and history will also be summarized in a separate table before and after implementing the protocol amendment 2.

**Pre-bronchodilator, post-bronchodilator tests, and reversibility at Screening** will be summarized as follows:

- Pre-bronchodilator tests:
  - FEV1
  - FEV1 % predicted
  - FVC
  - FVC % predicted
- Post-bronchodilator tests:
  - FEV1
  - FEV1 % predicted
  - FVC
  - FVC % predicted
  - Ratio of FEV1/FVC
- Change from pre-bronchodilator test:

- % bronchodilator reversibility
- Change from pre-test FEV1
- Reversible (Yes, No)

Pre-bronchodilator, post-bronchodilator tests, and reversibility at Screening will also be summarized in a separate table before and after implementing the protocol amendment 2.

FEV1 at baseline will be summarized descriptively. It will also be summarized in a separate table before and after implementing the protocol amendment 2.

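### Coding exacerbation history as none versus at least one in the primary model gives up a little precision that the collected count could recover at almost no cost

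*SAP*

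**What the plan says.** SAP 4.2.4.1 specifies a negative binomial regression with log exposure as offset. Besides treatment, baseline inhaled corticosteroid use and baseline COPD severity, it includes "history of at least one exacerbation in the past year, and smoking status as factors".

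SAP 4.2.2.2 lists, among the COPD history items to be summarised, both a yes/no item for the previous 12 months and the "Number of COPD exacerbations in the previous 12 months". The count is therefore available. No reason is given for modelling only the yes/no form.

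The same model is used for the on-study analysis of the primary endpoint (4.2.4.1) and for the hospitalization rate (4.2.4.2). Both follow the primary analysis in the sequential testing of 4.2.4. Appendix 1 builds its imputation model from the primary model with all its covariates.

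On power, SAP 1.3.2 states: "The sample size of 4,000 patients after 1 year of treatment will have ~89% power" for a rate ratio of 0.86, with a placebo rate of 0.8 per year, an overdispersion factor of 0.67, and "assuming a treatment discontinuation rate of 30% during the first year". No covariate is mentioned.

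**The concern.** Past exacerbation frequency would be expected to predict future frequency. If patients with two or more prior events exacerbate more often than patients with one, the two-level factor cannot show it. That between-patient variation then goes into the estimated dispersion k. In a negative binomial model k adds directly to the variance of the log rate ratio, so the interval for the treatment effect widens.

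What is at stake is precision on the primary efficacy test. To an extent not quantified here, it is also precision on the two tests gated behind it and on the Appendix 1 imputations.

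**Working it through.** **Step 1: reproduce the plan's figure.** Inputs from SAP 1.2, 1.3.2 and 4.2.4: n = 2,000 per arm (1:1), placebo rate 0.8, aclidinium rate 0.8 × 0.86 = 0.688, k = 0.67, two-sided 0.05, 30% first-year discontinuation. Assuming exponential discontinuation, mean exposure is t = 0.30 / (−ln 0.70) = 0.841 years.

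Var(log RR) = [1/(0.8t) + k + 1/(0.688t) + k] / n = [1.486 + 0.67 + 1.728 + 0.67] / 2,000 = 0.002277, so SE = 0.0477.

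Power = Φ(|ln 0.86|/0.0477 − 1.96) = Φ(3.161 − 1.960) = 88.5%. With t = 0.85 it is 88.7%, and with patient-level variable exposure 87.6%. The stated figure of about 89% reproduces without any covariate.

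**Step 2: how much does k matter?** In the same formula, lowering residual k from 0.67 to 0.60 gives 89.4%, and to 0.50 gives 90.8%. Power depends only weakly on residual overdispersion.

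**Step 3: gain when history and outcome share a patient-level propensity.** Negative binomial fits to 200,000 simulated patients per scenario, SE scaled to N = 4,000. Assumed: total overdispersion 0.67, mean prior count 0.5 to 1.5 per year, and a share of the between-patient variation that persists from the prior year.

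| Persistent share (assumed) | Variance ratio, two-level / (0, 1, ≥2) | Power gain, (0, 1, ≥2) | Power gain, (0, 1, 2, ≥3) |
|---|---|---|---|
| 0.3 | 1.000–1.004 | about 0.1 point | about 0.1 point |
| 0.6 | 1.008–1.017 | 0.1–0.4 | 0.2–0.6 |
| 0.9 | 1.009–1.035 | 0.4–1.0 | 0.5–1.5 |

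The largest variance ratio is 1.053, for the four-level coding at share 0.9 and mean prior count 1.5. That is a reduction of 1 − 1/1.053 = 5%. For the three-level coding the largest is 1 − 1/1.035 = 3.4%.

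**Step 4: gain when the prognostic strength is set directly.** Same rate, discontinuation and treatment effect, again 200,000 patients per scenario. Assumed: history mix 40/35/25% for 0/1/≥2, a rate ratio of 1.5 for one versus none, and k = 0.55 given history.

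| ≥2 vs 1 rate ratio (assumed) | Estimated k, two → three levels | Variance reduction | Power, two → three levels |
|---|---|---|---|
| 1.2 | 0.55 → 0.55 | 0.3% | 88.9 → 89.0% |
| 1.5 | 0.60 → 0.56 | 1.5% | 87.9 → 88.4% |
| 2.0 | 0.70 → 0.56 | 4.8% | 86.2 → 87.8% |
| 2.5 | 0.78 → 0.54 | 8.0% | 84.7 → 87.5% |

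Only the within-row differences reflect the coding. Power falls down the rows because each row assumes more heterogeneity than the last.

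Neither simulation includes COPD severity, inhaled steroid use or smoking status, which the model already contains. To the extent that these correlate with prior counts, the gain is smaller.

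**The case against.** The strongest reply is that this is a choice between two defensible codings. The two-level factor is prespecified and used consistently across the exacerbation models and subgroups. Randomisation protects the comparison, and the model estimates whatever heterogeneity remains. All of that stands.

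The size is also unanchored, since the history mix and the rate ratios are assumptions. The 8% case needs a two-level-model k of 0.78, above the planning value of 0.67. Appendix 1 also conditions on each patient's own observed count, which recovers part of the individual propensity there. These points limit the size of the gain but do not remove it.

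Three stronger readings are tempting but not supported:

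- **Conflict with the GOLD groups.** A reader might infer that the coding contradicts the risk grading in SAP 3.1.3. The higher-risk criterion there is "≥2 or ≥1 leading to hospital admission", so one hospitalised event counts with two or more. A 0/1/≥2 factor would not reproduce that grouping either. The grouping describes baseline status and does not specify a covariate.
- **Lost stated power.** The figure of about 89% reproduces without this covariate, so nothing promised is lost.
- **A biased or invalid test.** A coarser baseline covariate neither confounds a randomised comparison nor inflates type I error.

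**Conclusion.** The point holds as a modest efficiency gain, not as an error. The count is collected and the two-level factor leaves usable prognostic information out of the primary model. Under the assumed scenarios, finer coding cuts the variance of the log rate ratio by about 0 to 5%, worth about 0.1 to 1.5 power points. It reaches about 8%, or about 3 points, only with a rate ratio near 2.5 for two or more versus one prior event.

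These sizes rest on assumed history distributions and prognostic strengths that the SAP does not supply. Effects on the gated tests and on the imputations were not calculated. With about 4,000 patients, the change is unlikely to alter the primary conclusion unless the result is close to the boundary.

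**What to change.** Before unblinding, replace the two-level history factor in SAP 4.2.4.1 with the number of exacerbations in the previous 12 months in three levels (0, 1, ≥2). Carry it into the analyses that reuse the model: the on-study analysis, the hospitalization rate in 4.2.4.2, and Appendix 1. State how a patient recorded as having a history but no number will be classified. Keep the 0 versus ≥1 subgroup displays in 4.2.4.1 and 4.2.5.1.

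The three-level factor nests the current one, so the existing contrast is retained. The cost is a wording change, one extra parameter with about 4,000 patients, and no new data. If the sponsor prefers the two-level factor, one sentence giving the reason would be enough.

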### **Sensitivity analyses**

To assess the robustness to variations of the data assumptions underlying the primary analysis on the primary efficacy endpoint, several sensitivity analyses will be conducted as follows:

- Jump to reference (J2R) approach (see Appendix 1 for details)
- Copy reference (CR) approach (Keene et al, 2014; see Appendix 1 for details)
- Tipping point analysis (see Appendix 2 for details)

### **Subgroup analyses**

To evaluate the consistency in the primary efficacy endpoint over demographics and baseline characteristics, subgroup analyses will be performed. The subgroups are described below:

- Age group ( $\geq 40$  and  $< 60$  years,  $\geq 60$  and  $< 70$  years,  $\geq 70$  years old)
- Sex (Female, Male)
- Race (White, Other)
- Smoking status (Current smoker, Ex-smoker)
- Baseline ICS use (Yes, No)
- Baseline COPD severity (moderate, severe, and very severe)
- History of at least one exacerbation in the past year ( $0, \geq 1$ )

Exacerbation rate in aclidinium group will be compared to exacerbation rate in the placebo group for each subgroup (on-treatment analysis) using a negative binomial regression model. The response variable in the model will be the number of moderate or severe COPD exacerbations experienced by a patient during the first year of treatment. The model will include treatment group, each subgroup, and the interaction term. In order to adjust for the exposure for each patient, the natural logarithm of the exposure time (in years) during the first year of treatment (subtracting the time when a patient experienced COPD exacerbation) will be used as an offset variable.

The estimated treatment effect (i.e., the rate ratio of aclidinium over placebo) and corresponding 95% CI will be presented graphically.

In addition, the primary efficacy endpoint will be analyzed (on-treatment analysis) for the following 2 subgroups:

- LABA users (with and without ICS): include patients who took LABA and/or LABA/ICS during the treatment period.
- LABA/ICS users: include patients who took LABA/ICS during the treatment period.

That is, data for each subgroup will be extracted first, then do analysis on each set of data using the same approach as the corresponding primary analysis.

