## 1.2 Study design

This is a Phase IV, multicenter, randomized, double-blind, placebo-controlled, parallel-group study evaluating the effect of Acclidinium Bromide (a long-acting muscarinic antagonist delivered by the Pressair® dry powder inhalation [DPI] device) compared with placebo on long-term CV safety and COPD exacerbations in outpatients at least 40 years of age who have been diagnosed with moderate to very severe COPD (postbronchodilator % predicted forced expiratory volume in 1 second [FEV1] < 80% and FEV1/forced vital capacity [FVC] ratio < 70%) and a history of CV or cerebrovascular disease and/or significant CV risk factors.

Note: in this document

1. The term “double-blind treatment period” applies to the following 2 scenarios:
  - When used in “maximum of 36-months double-blind treatment period”
  - When used for patients who completed 36-months treatment (completer)
2. The term “during the treatment period” refers to on-treatment period.
3. The term “during the whole study period” refers to both on-treatment and off-treatment (post-treatment follow-up) periods.

The study consists of two-week washout/run-in period (for patients on a long-acting muscarinic antagonist [LAMA]) followed by a maximum of 36-month double-blind treatment period.

Signed informed consent form (ICF) from the patient or the patient’s legally authorized representative will be obtained before any study-related procedures are begun. All patients will be assigned a patient identification (PID) number via the interactive web response system (IWRS). Patients meeting the entry criteria for this study will be randomized (1:1) to acclidinium bromide 400 µg (abbreviated as acclidinium hereafter) twice a day (BID) or placebo BID. This study will conclude when 122 patients have experienced an adjudicated MACE.

Patients who prematurely discontinue investigational product (IP) will participate in a post-treatment follow-up period. The follow-up period will include on-site visits and telephone visits to collect MACE, COPD exacerbations, concomitant medications, and SAEs for the remainder of the study duration.

An independent Data Safety Monitoring Board (DSMB) will be established for this study. The DSMB will periodically monitor and review relevant clinical safety data, including adjudicated MACE.

Patients will be assessed according to the Schedule of Evaluations (See Section 2 of the clinical study protocol [CSP]).

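### The seven baseline subgroup models for the primary efficacy endpoint drop the primary model's prognostic factors without a reason, giving up a little precision and a strict like-for-like comparison

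*SAP*

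**What the plan says.** SAP Section 4.2.4.1 specifies the primary analysis as a negative binomial regression of moderate or severe exacerbations in the first year: "The model will include treatment group, baseline ICS use, baseline COPD severity", with exacerbation history and smoking status as further factors and log exposure time as the offset.

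Under Subgroup analyses, the same section lists seven factors for a consistency check: age group, sex, race, smoking status, baseline ICS use, baseline COPD severity and exacerbation history. Endpoint, on-treatment basis and offset are those of the primary analysis. The right-hand side is not: "The model will include treatment group, each subgroup, and the interaction term". Rate ratios and 95% CIs are to be shown graphically.

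The section then adds two subgroups, LABA users and LABA/ICS users, each analysed on its own extracted data by the primary approach, so these keep the covariates. The MACE subgroup in Section 4.2.5.1 also follows its primary model.

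**The concern.** A consistency check is cleanest when only the subgroup changes. Here the covariate adjustment changes too. For age, sex and race, all four primary factors drop out. For smoking, ICS use, severity and history, the factor itself stays as the subgroup main effect and the other three drop out.

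If the omitted factors predict exacerbations, their between-patient variation moves into the dispersion parameter and widens the subgroup intervals. Chance imbalance in those factors within a subgroup is also left uncorrected, so a subgroup estimate can sit slightly away from the adjusted overall estimate for a reason unrelated to effect modification. The SAP gives no reason for the reduced model, and the covariates are already derived for the primary analysis.

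**Working it through.** **Inputs from SAP Section 1.3.2.** "The sample size of 4,000 patients after 1 year of treatment will have ~89% power"; "rate ratio of 0.86 in acclidinium bromide relative to placebo) at 0.05 significance level"; "a placebo rate of 0.8 exacerbation per patient per year"; "overdispersion factor $k$ of 0.67"; "assuming a treatment discontinuation rate of 30% during the first year". Allocation is 1:1 (Section 1.2), so n = 2,000 per arm.

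**Step 1: reproduce the stated power.** With exponential discontinuation, mean exposure is t = 0.3/(−ln 0.7) = 0.841 years. The variance of the log rate ratio is

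Var = (1/n)[1/(t·r0) + 1/(t·r0·RR) + 2k].

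- 1/(0.841 × 0.8) = 1.486 and 1/(0.841 × 0.8 × 0.86) = 1.728, which sum to 3.214.
- Bracket = 3.214 + 2 × 0.67 = 4.554, so SE = √(4.554/2,000) = 0.0477.
- z = −ln(0.86)/0.0477 = 3.16, so power = Φ(3.16 − 1.96) = 88.5%.

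This matches the stated ~89%. Linear dropout (t = 0.85) gives 88.7%, and full information with variable exposure gives 87.6%.

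**Step 2: how omitted covariates enter.** The SAP does not say whether k = 0.67 is before or after adjustment. Take it as unadjusted. If the covariates give the patient-level rate a squared coefficient of variation c, the adjusted dispersion is 1.67/(1 + c) − 1. The sample size cancels from the ratio of interval widths (log scale), which is the square root of the ratio of the two brackets:

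| c | adjusted k | bracket | width, reduced/full |
|---|---|---|---|
| 0 | 0.670 | 4.554 | 1.000 |
| 0.05 | 0.590 | 4.395 | 1.018 |
| 0.10 | 0.518 | 4.251 | 1.035 |
| 0.20 | 0.392 | 3.998 | 1.067 |

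**Step 3: put assumed covariate effects in.** These are assumptions, since the SAP gives none. Rate ratios for history/severity/ICS use are 1.6/1.25/1.2, 2/1.3/1.3 or 2.5/1.4/1.4. Assumed prevalences are 60% with a history, 45% severe or very severe (treated as one step) and 50% on ICS. Smoking is given no effect. A binary factor with prevalence p and rate ratio r contributes p(1 − p)(r − 1)²/[1 + p(r − 1)]², and independent factors combine as the product of (1 + contribution).

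| assumed set | history | severity | ICS | combined c | full-model bracket |
|---|---|---|---|---|---|
| weak | 0.047 | 0.013 | 0.008 | 0.069 | 4.340 |
| moderate | 0.094 | 0.017 | 0.017 | 0.132 | 4.166 |
| strong | 0.150 | 0.028 | 0.028 | 0.215 | 3.963 |

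- History, severity and ICS use all omitted (age, sex, race, smoking): √(4.554/4.340) = 1.024, √(4.554/4.166) = 1.046, √(4.554/3.963) = 1.072.
- History subgroup, where history stays: k is 0.596, 0.527 and 0.453, and the reduced-model brackets are 4.405, 4.268 and 4.120. Ratios are 1.007, 1.012 and 1.020.
- Severity or ICS subgroup, where history is lost: about 1.02, 1.04 and 1.06 by the same formula.

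Prevalence matters a little. At 50% with a history, the strong set gives 1.083 in place of 1.072.

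**Step 4: simulation check of width and bias.** Trials of 4,000 (up to 60 per scenario) were simulated with sex as the subgroup, k = 0.67 as the dispersion left after adjustment, and all four covariates either omitted or included.

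| assumed covariates | width ratio | rate ratio, reduced vs full | SD of difference in log rate ratio |
|---|---|---|---|
| none | 1.000 | 0.845 vs 0.845 | 0.003 |
| weak | 1.009 | 0.864 vs 0.864 | 0.011 |
| moderate | 1.027 | 0.856 vs 0.861 | 0.019 |
| strong | 1.055 | 0.848 vs 0.845 | 0.024 |

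The estimates show no systematic shift. Single-trial differences are small beside a subgroup standard error of about 0.063 to 0.068.

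**The case against.** The strongest reply is that treatment, subgroup and interaction form a valid, prespecified model in a randomised trial. Section 4.2.4 treats CIs as descriptive, the subgroup text sets no interaction test or decision rule, and the precision at stake is small and could be zero. All of that stands, and it makes this an optional improvement.

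A reader might infer three stronger things that the SAP does not support:

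- **That the subgroup estimates are biased or not comparable with the overall result.** Endpoint, offset and on-treatment basis are the same. Under randomisation with a log link the rate ratio is close to collapsible, and the simulation shows no systematic shift.
- **That one display mixes adjusted and reduced-model estimates.** All seven baseline factors share one model form. The LABA subgroups were added later (October 2017 entry in the amendment history), are defined by use during treatment, and are not said to join the same graph.
- **That the remark in Section 5 about harmonised covariates makes this a contradiction.** It sits in a list of changes from the protocol and does not say that every model has identical factors. Models elsewhere in the SAP differ by endpoint.

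Convergence is also a fair point. Section 3.1.3 pools mild into moderate COPD to avoid a convergence problem, and Section 4.2.4.1 already provides a fallback model. A fuller subgroup model therefore carries a small added risk.

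**Conclusion.** The point holds as a minor one. The seven baseline subgroup models omit three or four primary-model factors for no stated reason, unlike the LABA and MACE subgroups. They target nearly the same rate ratio as the primary model, so the cost is precision and a strict like-for-like comparison.

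Intervals are about 2-7% wider for age, sex, race and smoking and about 1-2% wider for history. Severity and ICS use fall close to the first group. These sizes rest on assumed covariate effects and prevalences and on reading k = 0.67 as the unadjusted dispersion. There is no loss if the factors are not prognostic. The primary efficacy conclusion, its error rate and its power are untouched.

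**What to change.** In SAP Section 4.2.4.1, Subgroup analyses, replace the reduced model for the seven factors with the primary model (treatment, baseline ICS use, COPD severity, exacerbation history, smoking status, log-exposure offset) plus the treatment-by-subgroup interaction. Add the subgroup main effect only for age, sex and race, since the other four are already in the model. State that if this model does not converge, either the Poisson fallback in the same section or the current reduced model will be used.

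The cost is a sentence or two of text and no new derivations. With severity at three levels and the other factors at two, the primary covariates take 1 + 2 + 1 + 1 = 5 parameters. The change therefore adds 5 parameters for age, sex and race, 4 for smoking, ICS use and history, and 3 for severity, with a small convergence risk. If the reduced model is intended, one sentence of justification would close the point.
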